6.1. Intrarater Reliability

Intrarater reliability was assessed using Intraclass Correlation Coefficients (ICCs), based on a two-way mixed-effects model, single measures, with absolute agreement (ICC(3,1)).

Two independent sets of measurements by Rater 1 were averaged:

- Average 1 = Mean of M1 and M5
- Average 2 = Mean of M2 and M6

ICCs were calculated separately for the left and right hands.

Confidence intervals (95%) and F-tests were reported to assess the significance of the

ICCs. Interpretation followed Koo and Li's guidelines:

- ICC < 0.5 = poor
- $-0.5 \le ICC < 0.75 = moderate$
- $-0.75 \le ICC < 0.90 = good$
- ICC ≥ 0.90 = excellent

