Study Protocol

Validation Study of a Digital Measurement Device for Central Hand Representation in Children with Neonatal Brachial Plexus Palsy (NBPP)

NCT Number

NCT06950879

Researchers:

[name], [name], [name], [name]. [name]

Date: November 19, 2024

Version: 1.2

1. Introduction

Hand function is one of the most complex sensorimotor skills, requiring both motor output and multisensory input. The brain forms a complex representation of the hand using visual, proprioceptive, and anthropometric information.

This study focuses on **implicit hand representation**, which is influenced by non-visual afferent signals. In children with Neonatal Brachial Plexus Palsy (NBPP), this implicit hand representation appears to be disrupted, leading to altered hand function.

Previous research by [name] et al. showed that the reproducibility of existing test methods is good but that the procedures are cumbersome. This led to the development of the **HANDUZ prototype**, a digitized device that can automatically capture and process hand representation.

This validation study aims to evaluate the **reproducibility** of this prototype in children with NBPP. Reproducibility is measured both **intra-observer** and **inter-observer**.

2. Study Design

Type of study:

Validation study with reproducibility analysis

Design:

This is a single-center, observational reliability study involving children with a confirmed diagnosis of NBPP. Each participant completes six localization trials per hand using the HandUZ device. Two trained raters alternate administration to assess interrater and intrarater reliability. The study is conducted at the Child Rehabilitation Centre of Ghent University Hospital.

Population:

Participants: 18 children aged 8-18 years diagnosed with NBPP.

Inclusion and Exclusion Criteria:

- Inclusion: Children with a confirmed diagnosis of NBPP
- **Exclusion:** Children with other neurological, psychiatric, or physical disorders that could affect hand function

Measurement method:

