Participants are seated comfortably in front of a custom-built HandUZ setup, which consists of a three-layered vertical structure: a bottom plate with a measuring mat for hand positioning, a middle plate for visual occlusion, and a top plate holding an overhead webcam. The camera captures an image of the participant's hand for landmark annotation. The tested hand is placed palm-down on the measuring mat, and vision is occluded using the middle plate during the perceptual task.

Each hand is assessed six times in an alternating sequence by two trained raters, following a standardized protocol. The examiner verbally names specific anatomical landmarks—including the centers of the metacarpophalangeal (MCP) joints, fingertips, and wrist styloid processes—and the child uses the index finger of the contralateral (non-tested) hand to localize the

corresponding point on the occluded test hand. The examiner then digitally records the judged location on the computer interface.

The estimated finger length (FL) is calculated using the Euclidean distance between each fingertip and the corresponding MCP joint, as identified during the perceptual task. These values are averaged across two trials to obtain a representative estimated FL for each finger.

Separately, the actual FL is calculated from the image of the participant's hand (taken before the task), using the same anatomical landmarks. For each finger, the percentage overestimation (OE) is calculated using the following formula:

OE (%) = 100 × [(Estimated FL – Actual FL) / Actual FL]

Negative values indicate underestimation while positive values indicate overestimation.

To account for potential learning effects, non-consecutive trials are averaged (e.g., trials 1 and 5; 2 and 6). These averaged values are then used for reliability analyses.

3. Statistical methods

A detailed SAP is included in a separate section and outlines the statistical procedures for assessing reliability, learning effects, and assumption checks. All analyses were conducted using IBM SPSS Statistics (Version 29.0.2.0). A significance level of α = 0.05 was applied. ICC(3,1) was used for reliability analysis, and repeated-measures ANOVA assessed learning effects. Assumption checks included Shapiro-Wilk tests and Mauchly's test for sphericity.

4. Reporting of Results

- Tables: ICC values for intra- and inter-observer reproducibility with 95% confidence intervals

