- **Graphs:** Bland-Altman plots to visualize measurement differences and detect systematic bias
- **Conclusions:** Whether the HANDUZ system provides reproducible measurements for clinical use. High reproducibility would support its further clinical implementation.

5. Ethical Considerations

The study protocol was approved by the Ethics Committee of Ghent University Hospital (reference B6702024000525) and conducted in accordance with the Declaration of Helsinki. All participants and/or their legal guardians provided written informed consent.

6. Potential Limitations

- Small sample size (17 children) may limit generalizability
- Accuracy of reference point indication by participants may vary, introducing minor measurement errors

7. Study Timeline

• Participant recruitment: 2 months

• Data collection: 2 months

• Data analysis and reporting: 1 month

• Total study duration: ~5 months

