6.2. Interrater Reliability

Interrater reliability was evaluated using the same ICC model (ICC(3,1)). Average 3 (M2 and M5 by Rater 1) was compared with Average 4 (M3 and M4 by Rater 2). Separate ICCs were computed for each hand. Confidence intervals and significance levels were reported to quantify rater agreement.

7. Handling of Multiple Testing

This validation study focused on a limited number of predefined analyses, thus adjustments for multiple comparisons were not applied. Nevertheless, the potential for Type I error was minimized by restricting analyses to those aligned with the stated study objectives. Effect sizes (partial η^2) were reported alongside p-values for ANOVA results to aid interpretation and assess the magnitude of learning effects.

8. Software

All statistical analyses were performed using IBM SPSS Statistics (Version 29.0.2.0, IBM Corp., Armonk, NY, USA). Data preprocessing and visualization of hand maps were conducted using custom-built software in Python (Spider 3.0).

9. Significance Thresholds

All statistical tests were two-tailed. The threshold for statistical significance was set at:

- $\alpha = 0.05$
- Confidence intervals were set at 95%.
- For repeated-measures ANOVA, partial eta squared (η^2) was reported as the measure of effect size.

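### ICCs are split by left and right hand only, so if lesion side varies between children none is specific to the affected hand

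*SAP*

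**What the plan says.** SAP 6.1 (Intrarater Reliability) compares two averages of Rater 1's trials and states that "ICCs were calculated separately for the left and right hands". SAP 6.2 (Interrater Reliability) applies the same ICC model to Rater 1 against Rater 2 and states that "Separate ICCs were computed for each hand"; I read this as the same left/right split. Neither document mentions affected or unaffected hands. Lesion information appears only in SAP 3, among the demographic descriptives.

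Three parts of the protocol bear on this:

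- The eligibility line in section 2 reads "Inclusion: Children with a confirmed diagnosis of NBPP". It sets no condition on side and does not address bilateral lesions.
- The introduction gives the rationale: in these children "this implicit hand representation appears to be disrupted, leading to altered hand function".
- Under the measurement method in section 2, "the child uses the index finger of the contralateral (non-tested) hand" to point at the hidden hand.

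The conclusion planned in protocol section 4 is "Whether the HANDUZ system provides reproducible measurements for clinical use".

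**The concern.** With a one-sided lesion, a child is measured in two different situations. In one, the affected hand is the target and the unaffected hand points; in the other the roles swap. Both the representation being measured and the hand doing the pointing change. A left/right split separates these situations only if every child has the lesion on the same side. If the side varies, the left-hand ICC and the right-hand ICC are each a mixture of the two.

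A reader who wants to know how reproducible the device is when the affected hand is tested would then find no figure that answers. The blend could hide lower reliability in one situation. If the two situations differ in mean, it could also exceed the ICC of both. If they are equally reliable with equal means, nothing is distorted, but the planned output would not show that either.

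**Working it through.** **1. Number of hands.** SAP 2 counts 204 trials, 7 of them excluded (7/204 = 3.4%, as stated). Protocol section 2 gives six trials per hand. 204 / (2 hands × 6 trials) = 17 children, which agrees with the 17 in protocol section 6; the 18 in protocol section 2 would give 216 trials. Each ICC therefore rests on at most 17 hands, whether hands are grouped as left/right or, if all lesions are one-sided, as affected/unaffected.

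**2. Does side vary?** The documents do not say. As an illustration, suppose each lesion falls on a given side independently with probability q. All 17 then share a side with probability q^17 + (1 − q)^17: about 0.00002, 0.002 and 0.17 for q = 0.5, 0.7 and 0.9. If they did all share one side, one of the planned ICCs would be the affected-hand ICC and the point would fall away.

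**3. Blended ICC.** The documents give no ICC values, so every pair below is an assumption. Set the between-child variance to 1 in both situations. The error variance is then e = 1/ICC − 1. With a share p of hands in the higher-ICC situation and equal means,

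blended ICC = 1 / (1 + p·e₁ + (1 − p)·e₂).

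Example, 0.85 and 0.45 at p = 6/17: e₁ = 0.1765, e₂ = 1.2222; mean error = 0.353 × 0.1765 + 0.647 × 1.2222 = 0.853; blend = 1/1.853 = 0.540. A 6:11 side split puts p = 6/17 in one hand's ICC and p = 11/17 in the other's.

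| Assumed ICCs | p = 6/17 | p = 1/2 | p = 11/17 |
|---|---|---|---|
| 0.70 / 0.70 | 0.700 | 0.700 | 0.700 |
| 0.75 / 0.65 | 0.682 | 0.696 | 0.711 |
| 0.85 / 0.55 | 0.628 | 0.668 | 0.713 |
| 0.85 / 0.45 | 0.540 | 0.588 | 0.647 |

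On the SAP 6.1 bands (cut points 0.5, 0.75, 0.90), the last row is a good and a poor situation that both read as moderate. In the 0.85/0.55 row, the lower situation and the blend are both moderate, so only the higher label is lost. In the 0.75/0.65 row the blend is within 0.03 to 0.07 of both true values.

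If total variance rather than between-child variance is equal, the blend is p·ICC₁ + (1 − p)·ICC₂. That gives 0.656, 0.700, 0.744 for 0.85/0.55 and 0.591, 0.650, 0.709 for 0.85/0.45, all still moderate.

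**4. Mean shift.** Let both ICCs be 0.70 (error variance 0.4286) and let the means differ by d between-child SDs at p = 1/2. The blend is (1 + d²/4) / (1 + d²/4 + 0.4286) = 0.700, 0.713 and 0.745 for d = 0, 0.5 and 1. Pooling alone can lift the ICC above both true values.

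**5. What the added ICCs could show.** F-based 95% CIs for the single-measure, absolute-agreement ICC, with 17 hands, two averages and no systematic shift between them:

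| ICC | 95% CI |
|---|---|
| 0.55 | 0.121 to 0.808 |
| 0.70 | 0.355 to 0.879 |
| 0.85 | 0.641 to 0.942 |

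If a shift between the two averages makes up 20% of the error variance, the intervals are 0.318 to 0.882 at 0.70 and 0.591 to 0.946 at 0.85.

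In 20,000 simulated samples of 17 children, with a correlation between a child's two hands of 0 or 0.8, the affected and unaffected CIs failed to overlap in:

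- 0.5% or 0.2% of samples at 0.70/0.70;
- 1.3% or 0.6% at 0.75/0.65;
- 14.6% or 11.3% at 0.85/0.55;
- 25.2% or 22.1% at 0.85/0.45.

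**The case against.** The strongest reply is that nothing here is an error. The SAP's objective is reliability in children with this diagnosis, the planned conclusion concerns the system as a whole, and no section promises a statement about the affected hand. The point also depends on conditions that the documents do not establish: lesions are one-sided, side varies, and reliability or means differ between the situations. Disrupted representation concerns what is measured and does not by itself imply poorer repeatability. Protocol section 6 calls pointing errors minor and ties them to neither hand. Where the gap is small, the blend differs from the affected-hand value by far less than its sampling error. The direction is unknown too: testing the affected hand leaves the other hand to point, so the affected-hand ICC could be the higher one. Finally, the extra ICCs would be imprecise and added after the data were processed.

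Most of this stands, and it is why the point is optional. The left/right ICCs are not wrong, the size is unknown, and the added ICCs could not establish a difference. What it does not remove is the gap itself: if side varies, no planned ICC is specific to the situation that the study's rationale is about. The imprecision argument does not favour the planned split, since regrouping keeps up to 17 hands per ICC and so about the same nominal precision.

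**Conclusion.** The concern holds, conditionally. If lesions are one-sided and side varies, both planned ICCs mix two measurement situations and none describes testing of the affected hand. The text makes this clear, provided that SAP 6.2 uses the left/right split of SAP 6.1. The size is not known: under the assumed ICC pairs it runs from no effect, through a few hundredths, to good and poor both reported as moderate. It does not invalidate the left/right ICCs as summaries of this sample. It limits what can be said about the affected hand. I rate it as an improvement the study could make, with medium confidence.

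**What to change.** Keep the left/right ICCs and add the following to SAP 6.1 and 6.2:

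> Intrarater (Average 1 v 2) and interrater (Average 3 v 4) ICCs with 95% CIs are also given by affected and unaffected tested hand. They were added after trial exclusions, are descriptive, lie outside the predefined set in section 7, and do not test a difference.

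In SAP 3, report the distribution of lesion side and list any bilateral cases separately, outside the split. Base any statement about the affected hand on these ICCs.

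**Cost.** Four ICCs per outcome (2 analyses × 2 hands) become eight, from existing data. The SAP does not say whether ICCs are run per finger; if they are, over five fingers, 20 become 40. SAP 7 justifies making no multiplicity adjustment on the ground that "This validation study focused on a limited number of predefined analyses", and SAP 2 already reports exclusions, so the additions must be labelled as later and descriptive. Their intervals will be wide, and band labels drawn from them should be read with the CI. The split needs lesion side to have been recorded, which the lesion descriptives in SAP 3 may or may not include.

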6.2. Interrater Reliability

Interrater reliability was evaluated using the same ICC model (ICC(3,1)). Average 3 (M2 and M5 by Rater 1) was compared with Average 4 (M3 and M4 by Rater 2). Separate ICCs were computed for each hand. Confidence intervals and significance levels were reported to quantify rater agreement.

7. Handling of Multiple Testing

This validation study focused on a limited number of predefined analyses, thus adjustments for multiple comparisons were not applied. Nevertheless, the potential for Type I error was minimized by restricting analyses to those aligned with the stated study objectives. Effect sizes (partial η^2) were reported alongside p-values for ANOVA results to aid interpretation and assess the magnitude of learning effects.

8. Software

All statistical analyses were performed using IBM SPSS Statistics (Version 29.0.2.0, IBM Corp., Armonk, NY, USA). Data preprocessing and visualization of hand maps were conducted using custom-built software in Python (Spider 3.0).

9. Significance Thresholds

All statistical tests were two-tailed. The threshold for statistical significance was set at:

- $\alpha = 0.05$
- Confidence intervals were set at 95%.
- For repeated-measures ANOVA, partial eta squared (η^2) was reported as the measure of effect size.
